- ORR, DOR, and PFS based on HPV status and PD-L1 expressions (combined positive score [CPS] ≥ 1 and CPS ≥ 20)

Exploratory Endpoints:

- Response in injected and noninjected target lesions per intratumoral Response Evaluation Criteria in Solid Tumors (itRECIST) by Investigator assessment
- Baseline, and change from Baseline, in tumor or blood measurements of biomarkers related to TLR9, immune checkpoints, and potential markers of resistance or response to immunotherapy
- Change from Baseline in blood concentrations of C-X-C motif chemokine 10 (CXCL10) (IP-10) and other cytokines after treatment with CMP-001
- Blood concentrations of CMP-001 or its metabolites

Methodology:

This is a multicenter, open-label, Phase 2 clinical trial of CMP-001 administered by IT injection in combination with intravenous (IV) pembrolizumab in subjects with recurrent or metastatic head and neck squamous cell carcinoma (HNSCC) not previously treated with a PD-1 blocking antibody. This will be a Phase 2 study, with response and DOR assessments using RECIST v1.1 and iRECIST criteria according to Investigator assessment. All subjects will receive CMP-001 IT and pembrolizumab IV according to the treatment schedule until a reason for treatment discontinuation is reached.

Number of subjects (planned):

A total of 43 subjects is planned for this study. This is based on the following assumptions:

- A historical ORR of 19% with pembrolizumab monotherapy in subjects with HNSCC who have a CPS ≥ 1 and were not previously treated with a PD-1 blocking antibody (null hypothesis)
- An anticipated ORR of 35% with CMP-001 and pembrolizumab (alternative hypothesis).
- Power of 80% and one-sided alpha level of 0.05.

Diagnosis and main criteria for inclusion:**Inclusion criteria:**

Subjects enrolled in the study must meet all of the following inclusion criteria to be eligible:

1. Subjects with histologically- or cytologically-confirmed recurrent or metastatic HNSCC considered incurable by local therapies, and subjects with T4 or N3 disease who are ineligible for or refusing local therapies.
2. No prior systemic therapy in the recurrent or metastatic setting. Systemic therapy as part of multi-modal treatment for locally advanced disease is allowed.
3. Primary tumor locations of oropharynx, oral cavity, hypopharynx, larynx, paranasal sinus, or HNSCC of unknown primary origin. Participants may not have a primary tumor site of nasopharynx (any histology).

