9.1. Sample Size Calculation

The number of subjects planned for inclusion in this study is 43. Subjects who have provided written informed consent once the enrollment goal is reached may be allowed to complete Screening and enter study treatment if they meet all eligibility criteria, at the discretion of the Sponsor or its representatives. Subjects who discontinue the study before receiving the first dose of CMP-001 may be replaced to ensure at least 43 enrolled subjects.

A sample size of 43 achieves █ power to detect a difference of █ using normal approximation method at one-sided alpha level of 0.05, assuming that the null hypothesis for ORR is █, and the alternative hypothesis for ORR is █. The sample size calculation is performed in [PASS 2020](#) using the normal approximation to the binomial distribution.

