9.5. Efficacy Analyses

9.5.1. Confirmed Objective Response Rate

The primary efficacy endpoint for the study is the confirmed ORR based on RECIST v1.1 as determined by the Investigator.

The confirmed ORR is defined as the proportion of the subjects in the analysis set who have confirmed best response as CR or PR. The confirmed ORR will be calculated as the number of subjects with a confirmed CR or PR divided by the number of subjects in the analysis population [ORR = (cCR + cPR)/# subjects] for the ITT Analysis Set. For the ORR, 95% Clopper-Pearson confidence intervals will be calculated.

Subjects who discontinue due to death due to disease progression or disease progression, before having a post-Baseline tumor assessment will be classified as having a best response of PD. Subjects who discontinue before having a post-Baseline scan for other reasons will be counted as non-responders in the ITT analyses.

The primary efficacy analysis of confirmed ORR will be assessed according to RECIST v 1.1 by the Investigator for the ITT Analysis Set.

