Per Sponsor's decision, site activation and study enrollment were stopped earlier for any subjects who had not signed informed consent yet, and analyses were made exploratory. Consequently, the SAP will not necessarily be consistent with the protocol. In case of any discrepancies, this SAP will govern the analysis of data from this study.

II. Study Design

A. Design Overview

This is a multicenter, open-label, exploratory Phase 2 clinical trial of CMP-001 IT in combination with pembrolizumab IV in subjects with recurrent or metastatic HNSCC. Eligible subjects must have histologically- or cytologically-confirmed recurrent or metastatic HNSCC considered incurable by local therapies. All subjects will receive CMP-001 IT and pembrolizumab IV according to the treatment schedule until a reason for treatment discontinuation is reached.

CMP-001 10 mg will be administered weekly for 7 doses, after which it will be administered Q3W until the subject meets a condition for discontinuation of study treatment. The treatment will be given for a maximum of 2 years from the start of the study treatment. The first dose of CMP-001 may be administered SC or by IT injection, at the discretion of the Investigator; all subsequent doses are planned to be administered IT. The initial 7 CMP-001 doses on a weekly schedule must be completed before moving on to the Q3W CMP-001 dosing schedule.

If all injectable tumors regress, CMP-001 may be injected SC in the region of prior tumors or draining lymph node bed, at the Investigator's discretion (see Protocol Appendix F). On visits where both study drugs are administered, CMP-001 IT should be administered before pembrolizumab. CMP-001 should be administered until a reason for treatment discontinuation is reached, or for a maximum of 2 years from the start of the study treatment. See Protocol Section 5.1.2.4 for treatment modifications for CMP-001. Pembrolizumab 200 mg IV will be administered following CMP-001 10 mg IT injection at W1D1 and Q3W thereafter according to the KEYTRUDA® USPI. Pembrolizumab treatment during this study will continue until the subject meets a condition for discontinuation of study treatment.

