C. Sample Size Status

Given the early termination of site activation and study enrollment since 24Jun2022 per Sponsor's decision, all the analyses will be descriptive and exploratory. The number of subjects included in this study is 24. Subjects who have provided written informed consent once the enrollment goal is reached may be allowed to complete Screening and enter study treatment if they meet all eligibility criteria, at the discretion of the Sponsor or its representatives. As enrollment is terminated, subjects who discontinue the study before receiving the first dose of CMP-001 will not be replaced.

With the enrollment of the last subject on 22Jun2022, the subject status of this study is as follows:

- 39 subjects were screened
- 15 subjects were screen failures
- 24 subjects started the treatment

D. Treatment Randomization

No randomization will be performed in this study.

E. Assessment Schedule

See Protocol Table 1 for the study schedule of assessments.

F. End of Study

Per Sponsor's decision, site activation and study enrollment were terminated officially on 24Jun2022. All subjects previously enrolled in the study may continue receiving up to 2 years of study treatment per the current protocol.

The end of study is defined as the date of the last dose of study treatment for the last ongoing subject, plus 30 days of safety follow-up.

III. Protocol Objectives

Per Sponsor's decision, enrollment was stopped before reaching the sample size planned for the analyses described in the Protocol. All analyses will be exploratory. The performance of the statistical analysis for the protocol objectives and endpoints of the exploratory phase 2 study is contingent on the availability of the data source. Detailed information will be provided in the corresponding sections to follow.

Regeneron Pharmaceuticals Inc. / Protocol: CMP-001-007
IQVIA Biotech (Confidential) Project # SZA56629

A. Primary

- To determine the Investigator-assessed confirmed objective response with CMP-001 in combination with pembrolizumab in subjects with head and neck squamous cell carcinoma (HNSCC).

B. Secondary

- To evaluate the safety and tolerability of CMP-001 administered by intratumoral (IT) injection in combination with pembrolizumab in subjects with HNSCC.
- To evaluate the efficacy of CMP-001 in combination with pembrolizumab in subjects with HNSCC.

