Last date patient known to be alive from Long-Term Follow-Up eCRF	Use if patient status is reported to be alive. Do not use if patient status is not reported unknown
Post-treatment follow-up eCRF questions	Use if record selected
End of study	Not lost to follow up
Start/end dates from drug administration record	Nonmissing dose. Doses of 0 are allowed
Dosing prophylaxis eCRF	Prophylaxis given marked as yes
End of treatment date from the End of Treatment eCRFs	No condition
Tumor assessment (RECIST v1.1 or iRECIST) date	Evaluation is marked as done
Laboratory/PK collection dates	Sample collection marked as done
Vital signs date	At least 1 nonmissing parameter value
Physical examination	Evaluation performed marked as yes
12-Lead ECG	Evaluation performed marked as yes
ECOG performance status date	Nonmissing ECOG performance status
Start/end dates of adverse events	Nonmissing verbatim term
Start/end dates of concomitant medications and procedures	Nonmissing verbatim term

B. Primary Efficacy Analysis

The primary efficacy endpoint of ORR: The two-sided 95% CIs for the point estimates will be provided using Clopper-Pearson method.

A table summarizing the number and percentage of subjects with a Best Overall Response (BOR) of CR, PR, SD, PD, or Not Evaluable will be presented. This table will also include the ORR and DCR, with their two-sided 95% CI calculated using the Clopper-Pearson method.

Regeneron Pharmaceuticals Inc. / Protocol: CMP-001-007
IQVIA Biotech (Confidential) Project # SZA56629

C. Secondary Efficacy Analyses

The secondary efficacy endpoints include PFS, DOR, iORR, iPFS, iDOR and OS.

iORR. The two-sided 95% CIs for the point estimates will be provided using Clopper-Pearson method.

PFS, DOR, iPFS, iDOR, and OS. Estimates of median with 95% CIs will be computed using the Kaplan-Meier method. Kaplan-Meier curves will be plotted. Median Time-to-Event will be estimated at the 50th percentile of the corresponding Kaplan-Meier estimates. The event-free rate with the two-sided 95% CIs using Greenwood's formula will be calculated for 3-month interval timepoints (e.g., 6, 9, 12 and 18 months). The reasons for censoring will be summarized categorically with the number and percentage of subjects tabulated.

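### Does the protocol's 80% power for 43 subjects fail because no success rule is written down and no responder cutoff attains both stated figures?

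*Protocol*

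**What the plan says.** The Synopsis (Number of subjects) states that "A total of 43 subjects is planned for this study". It gives the assumptions as a historical ORR of 19% on pembrolizumab alone as the null, 35% on the combination as the alternative, and "Power of 80% and one-sided alpha level of 0.05". Section 9.1 repeats the sample size and the one-sided 0.05, and says the calculation was done "using the normal approximation to the binomial distribution". Its power and rates are blacked out, but the Synopsis supplies them.

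For the primary endpoint, Section 9.5.1 plans the proportion of confirmed responders among all treated subjects and adds: "For the ORR, 95% Clopper-Pearson confidence intervals will be calculated". SAP VIII.B does the same: "The two-sided 95% CIs for the point estimates will be provided using Clopper-Pearson method". Neither section names a test, a responder cutoff or a confidence limit to be compared with 19%.

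The SAP also records the early stop. Under I.B, "In case of any discrepancies, this SAP will govern the analysis of data from this study". Under II.C, "all the analyses will be descriptive and exploratory" and "The number of subjects included in this study is 24". SAP III says that enrollment ended short of the size planned for the protocol's analyses.

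**The concern.** Power and alpha are properties of a decision rule. The protocol quotes both but leaves the rule unwritten, and the only inference it plans for ORR is an exact interval, whereas the sizing used an approximation. Checked with exact binomial probabilities, no cutoff in 43 keeps alpha at or below 5% with power of at least 80%.

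Two natural readings of success also disagree at one result, 13 of 43 (30.2%). The z-test behind the sizing rejects 19% there, while the exact interval still covers 19%. If the exact interval were the yardstick, the trial would have 68.5% power, 11.5 points below the figure stated. A sponsor or reader could then take an inconclusive interval as a negative result from a well-powered study, or could choose the reading after seeing the data.

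**Working it through.** **Inputs.** From the Synopsis: n = 43, p0 = 0.19, p1 = 0.35, one-sided alpha 0.05, power 80%. From Section 9.1: normal approximation to the binomial. From Section 9.5.1 and SAP VIII.B: 95% Clopper-Pearson interval, denominator all treated subjects.

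**1. Reproduce the plan's figure.** Use the null variance in the rejection limit and the alternative variance for power:

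n = [(1.645 × √(0.19 × 0.81) + 0.842 × √(0.35 × 0.65)) / (0.35 − 0.19)]² = [(0.645 + 0.402) / 0.16]² = 42.8, rounded up to 43.

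Power at 43 = Φ[(√43 × 0.16 − 1.645 × 0.3923) / 0.4770] = Φ(0.847) = 80.1%.

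The stated size and power both reproduce. The variants tried do not give 43: continuity correction gives 49, alternative variance only 55, null variance only 38, arcsine 47, two-sided 0.05 54.

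**2. Find the cutoff this method implies.** The one-sided z-test rejects when the count exceeds 43 × 0.19 + 1.645 × √(43 × 0.19 × 0.81) = 8.17 + 4.23 = 12.40, so from 13 responders. As a check, z = (13 − 8.17) / 2.573 = 1.88 at 13, and (12 − 8.17) / 2.573 = 1.49 at 12.

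**3. Exact operating characteristics at n = 43.**

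| Success if responders ≥ | Exact alpha (ORR 19%) | Exact power (ORR 35%) |
|---|---|---|
| 12 | 10.1% | 87.3% |
| 13 | 5.19% | 79.1% |
| 14 | 2.42% | 68.5% |

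No row has alpha ≤ 5% and power ≥ 80%. The row implied by the declared method misses by 80 − 79.1 = 0.9 points of power and 5.19 − 5 = 0.19 points of alpha.

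**4. Where the 68.5% comes from.** Clopper-Pearson lower limits:

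| Responders of 43 | 95% interval | 90% interval |
|---|---|---|
| 13 | 17.2% | 18.9% |
| 14 | 19.1% | 20.9% |

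Used as a test against 19%, either interval needs 14. The whole difference between the two powers is the probability of exactly 13 responders when the true ORR is 35%: 79.1% − 68.5% = 10.6%.

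**5. What the plan will actually produce.** With 24 treated subjects, the SAP reports an ORR and its exact two-sided 95% interval. Neither calculation uses the 43, the 80% or a cutoff, so naming a rule for 43 subjects leaves both numbers as they are.

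**The case for a change.** The strongest case for a change is that the only inference planned is exact, so the exact figures are the honest ones, and that 43 is an unlucky size for an exact test. At 42 the exact one-sided 5% test needs 13 responders (alpha 4.3%, power 75.9%), which is more power than the 68.5% at 43. The first size that meets both stated figures exactly is 50, with 15 or more responders (alpha 4.1%, power 81.2%). The point does not depend on choosing the 95% level, because the exact one-sided 5% bound also needs 14. The missing rule is not an effect of redaction either, since Section 9.5.1 is not blacked out.

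All of this arithmetic stands. It does not show that the protocol's statement is wrong. The 68.5% belongs to a rule that neither document adopts: the interval is planned as estimation, and a two-sided 95% interval used as a test is a one-sided 0.025 rule, stricter than the 0.05 on which the trial was sized. Sizing by an approximation and reporting an exact interval is common practice and not a contradiction.

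A second argument is that a reader might carry the 80% over to 24 subjects. At a true ORR of 35%, the chance of excluding 19% would then be 31% (95% interval, 10 or more), 47% (exact one-sided 5%, 9 or more) or 64% (z-test, 8 or more, alpha 7.0%). These describe tests that nobody plans, and SAP II.C and III already say that the planned size was not reached and that the analyses are exploratory.

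**Conclusion.** The concern does not call for a change. The 43 subjects and 80% power are correct under the declared method, and the cutoff that method implies, 13 of 43, has exact alpha 5.2% and power 79.1%. That is ordinary binomial discreteness of about one point, not a design error. What remains is a cutoff left implicit, which an analyst can derive from the stated null, alpha and method.

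The larger figure of 68.5% is conditional on treating the exact interval, or an exact one-sided 5% test, as the success criterion. The documents do not say so.

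No result depends on the choice. The SAP governs, is descriptive and covers 24 subjects, so a 13-of-43 outcome cannot occur. Naming a cutoff after enrollment has closed, in an open-label trial with Investigator-assessed response, would also not be true prespecification. A note of the exact figures beside the sizing statement would be harmless, but it would change no estimate, interval or conclusion.

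This rests on reading the blacked-out figures in Section 9.1 as those in the Synopsis, and on the SAP remaining without a formal test of ORR.

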eCRF	electronic case report form
EOT	end of treatment
FDA	Food and Drug Administration
FSH	follicle stimulating hormone
GCP	Good Clinical Practice
HCC	hepatocellular carcinoma
HNSCC	head and neck squamous cell carcinoma
HPV	human papillomavirus
HRT	hormonal replacement therapy
IB	Investigator's Brochure
ICF	Informed Consent Form
ICH	International Council for Harmonisation

Abbreviation or Specialist Term	Explanation
ID	identification
IEC	Independent Ethics Committee
IFN	interferon
INR	international normalized ratio
IRB	Institutional Review Board
iCPD	immune confirmed progressive disease
iCR	immune complete response
iORR	immune objective response rate
iPFS	immune progression-free survival
iPR	immune partial response
iRECIST	immunotherapy Response Evaluation Criteria in Solid Tumors
itRECIST	intratumoral Response Evaluation Criteria in Solid Tumors
iSD	immune stable disease
IT	intratumoral(ly)
ITT	intent-to-treat
iUPD	immune unconfirmed progressive disease
IV	intravenous
LTSFU	long-term survival follow-up
MedDRA	Medical Dictionary for Regulatory Activities
MRI	magnetic resonance imaging
ODN	oligodeoxynucleotide
ORR	objective response rate
OS	overall survival
PD	progressive disease
PD-1	programmed cell death protein 1
pDC	plasmacytoid dendritic cell
PD-L1	programmed death-ligand 1
PET	positron emission tomography
PFS	progression-free survival
PTFU	Posttreatment Follow-Up
PR	partial response
PS20	polysorbate 20
PT	protime
PTT	partial thromboplastin time

Abbreviation or Specialist Term	Explanation
Q3mo	every 3 months
Q3W	every 3 weeks
Qb	Qbeta
QTc	QT corrected
RBC	red blood cell
RECIST	Response Evaluation Criteria in Solid Tumors
SAE	serious adverse event
SAP	statistical analysis plan
SC	subcutaneous(ly)
SD	stable disease
SOC	system organ class
SOP	standard operating procedure
TEAE	treatment-emergent adverse event
TLR9	toll-like receptor 9
ULN	upper limit of normal
UPD	unconfirmed progressive disease
US	United States
USPI	United States Prescribing Information
VLP	virus-like particle
WBC	white blood cell
WNL	within normal limits

1. INTRODUCTION

1.1. Background

This is a Phase 2 study to evaluate the safety and efficacy of intratumoral (IT) CMP-001 in combination with intravenous (IV) pembrolizumab in subjects with head and neck squamous cell carcinoma (HNSCC) with tumors that have a programmed death-ligand 1 (PD-L1) combined positive score (CPS) ≥ 1 .

Head and neck cancer is the seventh leading cancer by incidence worldwide with approximately 890,000 new cases and 450,000 deaths each year (Bray et al 2018). Squamous cell carcinomas of the head and neck constitute 90% of all head and neck cancers and are the ninth leading cancer by incidence worldwide (Jemal et al 2007; Gupta et al 2016). Head and neck cancers include cancers of the lip, oral cavity, oropharynx, hypopharynx, nasopharynx, larynx, as well as paranasal tumors, ethmoid sinus tumors, maxillary sinus tumors, salivary gland tumors, and mucosal melanoma head or neck tumors. In the United States, it is estimated that approximately 65,630 new cases of oral cavity, pharyngeal, and laryngeal cancers will occur in 2020, which account for approximately 3.6% of new cancers. An estimated 14,500 deaths from head and neck cancers will occur in the United States in the same time period (Siegel et al 2020).

Heavy use of alcohol and tobacco are typical etiologic factors in older patients. Human papillomavirus (HPV) infection, a well-accepted cause of squamous cancers of the oropharynx, has become more common, particularly in younger patients in North America and northern Europe (Chow 2020). The incidence of HPV-negative cancer has decreased; however, the overall incidence of HPV-positive head and neck cancers has increased in the United States, with the proportion of head and neck cancers diagnosed as HPV-positive rising from 16.3% in the 1980s to 72.7% in the 2000s (Chaturvedi et al 2008; Chow 2020). While oral HPV type 16 infection is the primary cause (Agalliu et al 2016; Gillison et al 2000; Gillison et al 2012; Ndiaye et al 2014), HPV types 18, 31, and 33 are responsible for the remaining HPV-related head and neck HPV-positive cancer (Snow and Laudadio 2010) and these primarily occur in younger patients. Two methods are used to detect HPV, polymerase chain reaction and p16 immunohistochemistry (IHC), with International Council for Harmonisation (ICH) testing being the more accessible established method (Duncan et al 2013).

NCCN guidelines on head and neck cancers (NCCN 2020) focused on head and neck cancers recommends participation in clinical trials for all patients with very advanced head and neck cancers. All combined chemoradiotherapy regimens are associated with mucosal toxicities. For patients with an ECOG Performance Status of 0 or 1, the NCCN guidelines on head and neck cancers (NCCN 2020) for newly diagnosed, very advanced disease is concurrent systemic/radiation therapy (with high-dose cisplatin and 5 fluorouracil [5-FU]) being a Category 1 option.

Response rates to systemic therapies range from 15% to 35% in patients with metastatic disease at initial presentation. In many circumstances, combination regimens result in a doubling of response rates compared to single agents but the median survival with systemic therapy is short (approximately 6 months) and a low 1-year survival rate of approximately 20% (NCCN 2020).

In KEYNOTE-048, pembrolizumab was evaluated as a first-line systemic treatment for patients with untreated, locally incurable recurrent or metastatic HNSCC (Burtness et al 2019). In this study, patients were randomized to receive pembrolizumab 200 mg every 3

weeks (Q3W) as a single agent (n = 300, monotherapy), the combination of pembrolizumab and chemotherapy consisting of a platinum and 5-FU (n = 276), or the combination of cetuximab, platinum, and 5-FU (n = 287, referred to as the EXTREME regimen). There was an overall survival (OS) advantage observed in the arm treated with the combination of pembrolizumab and chemotherapy with a median OS of 13 months compared to the EXTREME regimen with a median OS of 10.7 months ([KEYTRUDA United States Prescribing Information \[USPI\]](#)). Importantly, an OS advantage was also observed in patients with a PD-L1 CPS of both ≥ 20 and ≥ 1 for patients who received pembrolizumab monotherapy with a median OS of 14.9 months compared to those receiving the EXTREME regimen, where a median OS of 10.7 months was observed. The ORR for pembrolizumab monotherapy was 19% and 23% for the CPS ≥ 1 and CPS ≥ 20 groups, respectively, which was lower than the ORR observed with the EXTREME regimen of 35% and 36%, respectively. However, pembrolizumab monotherapy led to durable responses with a median duration of response (DOR) of 20.9 months for both CPS groups, which was longer than the 4.5 months and 4.2 months for the CPS ≥ 1 and CPS ≥ 20 groups in the EXTREME group, respectively.

In KEYNOTE-048, pembrolizumab was discontinued for adverse reactions in 12% of patients in the pembrolizumab monotherapy arm. The most common adverse reactions resulting in permanent discontinuation of pembrolizumab were sepsis (1.7%) and pneumonia (1.3%). Adverse reactions leading to the interruption of pembrolizumab occurred in 31% of patients. The most common adverse reactions leading to interruption of pembrolizumab ($\geq 2\%$) were pneumonia (2.3%), pneumonitis (2.3%), and hyponatremia (2%). Based upon these safety and efficacy data, FDA approved pembrolizumab as first-line treatment for recurrent, unresectable, or metastatic HNSCC as monotherapy in patients with PD-L1 positive expressed tumors or when combined with a platinum and 5-FU. Despite this important advance, the majority of patients who received pembrolizumab did not achieve a response, and significant unmet need remains for new agents and combinations that achieve durable responses and prolong survival.

